We will randomly select a subset of 30 samples from patients with similar overall 16S abundance, but 15 samples will have abundant *LBP* and 15 additional samples will have undetectable *LBP*. We will utilize the Illumina HiSeq2000 platform, aiming for a mean of 10 gigabases of 101 bp paired-end reads per sample. For comparative quantification of gene content at the individual gene level and the level of KEGG metabolic pathways, we will utilize linear discriminate analysis (LDA) effect size (LEfSe) analysis⁸⁹ for biomarker discovery. In addition to comparing samples with abundant and reduced *LBP* levels, we will also examine samples from patients who did or did not develop aGvHD. With this approach, we hope to identify novel bacterial genes and gene pathways, some of which may be *LBP*-derived, that are associated with modulation of aGvHD and may play a role in aggravating or attenuating inflammation. As all correlative assays will be performed on the backbone of a COG clinical trial, we anticipate high quality and very complete assessment laboratory findings.

7.3.3.2 **Evaluating the effects of LBP introduction on intestinal flora function via functional metabolite profiling**

While whole shotgun metagenomic sequencing provides information regarding the functional potential of the intestinal flora, a complementary approach is to assay directly for demonstration of substrate utilization and metabolite production. By determining bacterial metabolite abundances, one can confirm that increased abundance of individual genes and genes of metabolic pathways are associated with a corresponding increase in enzymatic activity. This method can also identify novel bacterial metabolites that are biologically active. One example of a group of metabolites that have garnered interest recently is short-chain fatty acids (SCFA), which are produced by many bacteria as a byproduct of carbohydrate fermentation. SCFA have been found to be important modulators of the immune system. In germ-free mice and vancomycin-

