treated conventional mice, administration of SCFA (acetate, propionate, or butyrate) restored normal numbers of Tregs in the large intestine.⁸⁴ GPR43 (a SCFA receptor) has been identified as necessary for mediating the anti-inflammatory effects of commensal bacteria⁹⁶ and is required for restoration of large intestinal Tregs by SCFA.⁸⁴ We will quantitatively profile levels of enzymatic substrates and metabolites via UHPLC-MS services coupled with an extensive library with >2800 authenticated compounds provided by Metabolon (Durham, NC). We will profile aliquots of the same stool samples selected for the whole shotgun metagenomic sequencing approach detailed above as well as paired serum samples collected at the same time as the stool samples. A recent study linking intestinal flora with severity of an autism-like syndrome in mouse models similarly utilized Metabolon's services to identify a serum metabolite that induced anxiety-like behavior in these mice. Interestingly, the levels of this metabolite were modulated by intestinal flora composition.⁹⁷ Using this approach, we will **identify novel bacterial metabolites, some of which may be LBP-derived, that are associated with modulation of aGvHD** and may play a role in either aggravating or attenuating inflammation.

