7.4 Specimen Collection, Processing and Shipping

7.4.1 Blood Specimens (Citrulline and Cytokines)

Sample Time Points:
	
 • First day of conditioning or anytime within 72 hours before the start of conditioning (prior to chemotherapy) • Day 0 (graft infusion) • Day 7 • Day 14 • Day 28 or discharge, whichever is first • Day 56 (citrulline only) 
Sample acquisition can occur within 72 hours before the first day of conditioning. Sampling can occur within 24 hours before or after designated collection times for D0, D7, D14, D28 without being considered a protocol deviation. D56 sampling can occur within 14 days without being considered a deviation.
								

Blood Collection Procedure:
	
Draw 6 mL of whole blood in a red top tube (supplied by site).
								

Specimen Processing:
	
 1. After collection, allow blood to coagulate at room temperature. 2. After coagulation (but within 1 hour after collection) centrifuge the blood samples at 4°C for 15 minutes at 3000 rpm. 3. Aliquot the serum (upper layer) into three 1.5 mL cryovials (0.5 mL of serum per aliquot). 4. Store frozen at -80°C (or -70°C) immediately after aliquoting. 								

Specimen Labeling:
	
Freezer-safe labels will be provided in specimen kits and must be used as specified in the Specimen Collection Manual. Each cryovial must be legibly labeled with: ACCL1633, COG Patient ID, Timepoint + Aliquot ID (to track individual vials), and Collection Date.
								

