Exploratory Aims 3 and 4: These aims will examine the effects of *LBP* introduction on the intestinal flora of pediatric alloHCT recipients. The association between *LBP* administration and bacterial genes and pathways, and bacterial metabolites will be evaluated with Pearson's correlation coefficient with possible transformation to approximate normality. In addition to confirming the significance, a 95% confidence interval will be estimated for each marker. The total length of the interval depends on the observed correlation; the length will be 0.53 if the correlation is 0.40 and 0.24 if the correlation is 0.8. In addition to correlation, bivariate scatterplots will be used to display the association between *LBP* administration and each marker. Finally, we will perform a descriptive analysis examining the association between GvHD outcomes and bacterial genes, pathways, and metabolites using Cox regression. Additional regression models will adjust for other known GvHD risk factors.

Exploratory Aim 5: This aim will examine the effects of *LBP* on pro-inflammatory cytokines in alloHCT recipients. We hypothesize that *LBP*-associated maintenance or restoration in the microbiota will attenuate serum levels of pro-inflammatory cytokines in the early post-transplant period. We will use the same analytic approach as described for exploratory Aim 2 above.

Exploratory Aim 6: This aim will examine the effects of LBP on the incidence (yes/no) of *Clostridium difficile*-associated diarrhea in alternative donor HCT patients. Patients who have at least one incidence (positive) of *C. diff* during any reporting period is considered evaluable for this aim. We will compare proportion of *C. diff* during the study period between arms via the chi-square test.

Exploratory Aim 7: This aim will examine whether LBP administration reduces hospital days within the first 120 days post hematopoietic cell transplant. Total hospital days over the study period is calculated as the duration between the date of admission for conditional therapy and the date of discharge (or the study end date). Hospital days will be compared between arms by t-test (or Wilcoxon rank-sum test if assumptions for t-test are not met).

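### The 30 stools for metagenomics and metabolites are picked by measured LBP, but Section 9.3 plans Pearson correlations with an undefined LBP administration variable; its interval lengths do not fit 30 samples, and the draw does not exclude visits without full serum.

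*Combined protocol and SAP*

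**What the plan says.** Exploratory Aim 1.2.4 asks for the effects of LBP on intestinal flora function, and the titles of Sections 7.3.3.1 and 7.3.3.2 both speak of effects of LBP introduction.

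Section 7.3.3.1 describes the samples: "We will randomly select a subset of 30 samples from patients with similar overall 16S abundance, but 15 samples will have abundant" LBP, while "15 additional samples will have undetectable" LBP. It does not mention randomized arm or visit. It analyses them with LEfSe and describes two contrasts: LBP level ("In addition to comparing samples with abundant and reduced" LBP levels) and aGvHD versus no aGvHD.

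Section 7.3.3.2 profiles metabolites in aliquots of the same stools "as well as paired serum samples collected at the same time as the stool samples".

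Section 9.3, Exploratory Aims 3 and 4, describes a different analysis. The association of LBP administration with genes, pathways and "bacterial metabolites will be evaluated with Pearson's correlation coefficient with possible transformation to approximate normality". It adds that "a 95% confidence interval will be estimated for each marker", with a total length of 0.53 at a correlation of 0.40 and 0.24 at 0.8. It gives no sample size and does not say whether LBP administration means assigned arm, doses taken or LBP measured in stool.

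Stool is collected at seven time points, the last on Day 120 (Section 7.4.2). Blood is collected at six, the last being "Day 56 (citrulline only") in Section 7.4.1.

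**The concern.** LBP measured in stool is a post-randomization variable. Choosing samples at its two extremes and then reporting a correlation with LBP administration mixes two questions: what the product does, and what goes with having much or no LBP in the stool. Randomization protects only the first.

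Pearson's r also depends on the spread of the variable. A sample with the middle range removed has a larger spread than the population, so its r and interval do not estimate the population correlation. Half the LBP values would be tied at the detection limit by design, which no transformation makes normal.

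At stake is the interpretation of the only functional analysis of the flora. Its results could be read as effects of LBP with a precision that 30 samples do not give, and the stool-serum pairing could be incomplete.

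**Working it through.** **1. The plan's interval lengths.** Inputs: r = 0.40 and 0.8, 95% level, stated lengths 0.53 and 0.24 (Section 9.3); n = 30 (Section 7.3.3.1). Fisher z: length = tanh(atanh r + 1.96/√(n−3)) − tanh(atanh r − 1.96/√(n−3)).

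- n = 40, half-width 1.96/√37 = 0.322. For r = 0.40, limits 0.101 and 0.633, length 0.53. For r = 0.8, limits 0.651 and 0.890, length 0.24. Both stated figures are reproduced, and 40 is the only n that fits both at 95%.
- n = 30, half-width 1.96/√27 = 0.377. For r = 0.40, limits 0.046 and 0.665, length 0.62. For r = 0.8, limits 0.618 and 0.901, length 0.28.

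The stated lengths would also fit n = 29 at the 90% level (0.532 and 0.239), but the text says 95%.

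**2. If the variable is measured LBP.** Assume bivariate normality with true correlation ρ, and keep only the outer fraction p on each side, cut at ±c. The variance of LBP among the selected is V = 1 + c·φ(c)/p, and r becomes ρ√V / √(1 + ρ²(V−1)).

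- Outer thirds: c = 0.431, V = 1.47. ρ = 0.30 becomes 0.36; 0.40 becomes 0.47.
- Outer quarters: c = 0.674, V = 1.86. ρ = 0.30 becomes 0.39; 0.40 becomes 0.51.
- Outer tenths: c = 1.282, V = 3.25. ρ = 0.30 becomes 0.49; 0.40 becomes 0.62.

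This version has no ties. A simulation with a latent ρ of 0.40 and the low values set to the detection limit gives, for the full censored sample against equal-sized extreme groups:

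- 50% undetectable, top 25% abundant: 0.34 becomes 0.42.
- 50% undetectable, top 10% abundant: 0.34 becomes 0.49.
- 25% undetectable, top 25% abundant: 0.38 becomes 0.49.
- 60% undetectable, top 20% abundant: 0.32 becomes 0.41.

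The plan sets no cut-off for abundant, so these fractions are assumptions.

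**3. If the variable is assigned arm.** Allocation is 1:1 (Section 9.2). Assume, for illustration, 75% detection in the LBP arm (the pilot's 77/102 *Lactobacillus*-positive stools, at genus level) and 10% under placebo (the adult series in Section 7.3.2.1).

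- Share of detectable stools from the LBP arm: 0.75/(0.75 + 0.10) = 88%.
- Share of undetectable stools from the LBP arm: 0.25/(0.25 + 0.90) = 22%.
- Stools in the group opposite to their arm, taking the 15 abundant at random from the detectable: 15 × 0.12 + 15 × 0.22 ≈ 5 of 30. Detection of 90%/10% gives 3; 60%/20% gives about 9.

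The simulated effect on r depends on mechanism, here at 75%/10%. If the marker rises with LBP level and abundant means the upper half of detected samples, r with arm goes from 0.27 to 0.41. If the marker depends only on detected or not, r is about unchanged (0.24 against 0.25). If the marker is driven only by a common cause that also lowers LBP, such as antibiotics, a true arm correlation of 0 becomes 0.14, or 0.08 to 0.16 over the detection rates tried, again with abundant as the upper half. With neither association nor common cause, r stays at 0.

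**4. Serum.** The plan gives no distribution of picks over visits. If the 30 are spread evenly over seven stool visits (assumption), 30/7 = 4.3 are Day 120 stools with no blood draw, and the chance of at least one is 1 − (6/7)^30 = 99%. If Day 120 picks fall only among the 15 undetectable stools, 15/7 = 2.1 are expected, with a 90% chance of at least one. Counting Day 56 as well, 60/7 = 8.6 of 30 lack serum designated for anything beyond citrulline.

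**The case against.** Sampling extreme groups is a reasonable way to spend 30 assays on discovery, and Section 7.3.3 presents the work as discovery. The LEfSe contrast in Section 7.3.3.1 is a proper two-group comparison on measured LBP. The sentence in Section 9.3 speaks of association. The inflation (0.06 to 0.09 for a true 0.30 with outer thirds to quarters) is small beside an interval of length 0.62. All of this stands, and it limits the weight of the point.

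A reader might infer more than the documents support:

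- *That Section 9.3 states Pearson will be run on the 30 stools.* It does not, and its interval lengths imply 40. The link is an inference, drawn because no other source of gene, pathway or metabolite data is described.
- *That the correlations are inflated whatever the variable.* This is clear only for measured abundance. For assigned arm it depends on mechanism, and in the censored simulation part of the rise only offsets attenuation at the detection limit: the selected values are 0.41 to 0.49 against a latent 0.40.
- *That Section 7.3.2.1 predicts that undetectable LBP in the active arm marks antibiotic exposure.* It predicts loss of commensal LBP in patients colonized at baseline who need broad-spectrum antibiotics, and better recovery with the product. Antibiotic confounding is plausible but not stated.
- *That some picked stools will certainly lack serum.* The pairing clause can be read as a selection condition, and Day 56 blood is drawn with no smaller volume specified. The text supports only that Day 120 and Day 56 are not excluded.

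**Conclusion.** The point holds in this form. The only samples described for the gene, pathway and metabolite data are selected on measured, post-randomization LBP, and Section 9.3 plans an analysis that does not fit them. The resulting r would be neither a randomized-arm effect nor, for measured LBP, a population correlation. In the measured case the overstatement is about 0.06 to 0.09 for a true 0.30 (outer thirds to quarters, bivariate normal). In the assigned-arm case the size and even the presence of bias depend on mechanism. The mismatch in interval lengths needs no assumption beyond the Fisher method: 0.53 and 0.24 stated, 0.62 and 0.28 at n = 30. The serum gap is a likely outcome of an unrestricted draw, not a stated fact. The aim is exploratory, and neither the primary analysis nor the safety aim depends on it. It is worth settling before samples are drawn, because the draw cannot be repaired afterwards.

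**What to change.** - In Section 9.3, drop Pearson r and its interval for the 30 selected samples. Analyse them as the abundant-versus-undetectable contrast that Section 7.3.3.1 already sets up, by LEfSe or by Wilcoxon test with a Hodges-Lehmann interval.
- Label the result in both sections as an observational association with measured LBP, not an effect of LBP administration. If LBP administration is used as a variable anywhere else, define it.
- Remove the stated interval lengths, or restate them with the n they refer to (0.62 and 0.28 for n = 30).
- Limit picks to on-treatment visits with both stool and full serum: Day 0 to Day 28 or discharge. The first stool is taken on the first day of conditioning or up to 72 hours before, when dosing is only starting (Sections 4.2.1 and 7.1), so it is essentially a pre-dose sample.

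The cost is wording and a revised draw list, with the same number of assays. The downside is fewer eligible stools and no late-visit samples. Drawing equal numbers per arm is an option if a randomized comparison of flora function is wanted, but it reduces the contrast in LBP abundance; that is a design trade-off, not a correction.

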7.3.4 Serum cytokines

To measure proposed immunomodulatory effects of *LBP* as decreases in mean serum levels of alloreactive-induced inflammatory cytokines and of aGvHD-associated GI insult in patients receiving *LBP* prophylaxis compared to patients receiving placebo. Specifically, TNFR1, ST2 and REG3 α will be analyzed given their previous validation as early biomarkers for aGvHD initiation and severity.⁹⁸ Furthermore, the concentrations of ST2 and REG3 α on day 7 post-BMT strongly correlate with the development of GVHD-related mortality, steroid-refractory GVHD, grade III/IV GVHD and GI GVHD stage 3/4.⁹⁹ Serial serum biomarker levels will be evaluated from the initiation of therapy to Day 30. We expect that patients who do not develop GVHD will have lower levels of these biomarkers on Days 7 and 14 than patients who develop GVHD. Alloreactive-induced inflammation in the early post-transplant period activates recipient antigen-presenting cells, which, in turn, instruct donor T-cells in the allograft to produce cytotoxic soluble factors like TNF α and IFN γ that cause damage to the GI epithelium. As maintaining tolerance within the GI tract is an established function of the gut microbiota, *LBP* prophylaxis may induce tolerogenic effects, blunting allo-induced inflammation and subsequent tissue damage in transplant recipients. Therefore, we hypothesize that *LBP*-associated maintenance or restoration in the microbiota will attenuate serum levels of pro-inflammatory cytokines in the early post-transplant period. Specifically, patients receiving *LBP* prophylaxis will have reduced serum levels of inflammatory cytokines compared to control patients.

7.4 Specimen Collection, Processing and Shipping

7.4.1 Blood Specimens (Citrulline and Cytokines)

Sample Time Points:
	
 • First day of conditioning or anytime within 72 hours before the start of conditioning (prior to chemotherapy) • Day 0 (graft infusion) • Day 7 • Day 14 • Day 28 or discharge, whichever is first • Day 56 (citrulline only) 
Sample acquisition can occur within 72 hours before the first day of conditioning. Sampling can occur within 24 hours before or after designated collection times for D0, D7, D14, D28 without being considered a protocol deviation. D56 sampling can occur within 14 days without being considered a deviation.
								

Blood Collection Procedure:
	
Draw 6 mL of whole blood in a red top tube (supplied by site).
								

Specimen Processing:
	
 1. After collection, allow blood to coagulate at room temperature. 2. After coagulation (but within 1 hour after collection) centrifuge the blood samples at 4°C for 15 minutes at 3000 rpm. 3. Aliquot the serum (upper layer) into three 1.5 mL cryovials (0.5 mL of serum per aliquot). 4. Store frozen at -80°C (or -70°C) immediately after aliquoting. 								

Specimen Labeling:
	
Freezer-safe labels will be provided in specimen kits and must be used as specified in the Specimen Collection Manual. Each cryovial must be legibly labeled with: ACCL1633, COG Patient ID, Timepoint + Aliquot ID (to track individual vials), and Collection Date.
								

Specimen Packaging and Shipping:
	
Samples should remain frozen at -80°C (-70°C is permitted) until ready for shipping. Batched shipment after each participant's completion of all specimens is strongly encouraged. Be sure to include enough dry ice in the shipment to last 48 hours. Prior to shipment, the lab should be notified by e-mail with a copy of Specimen Transmittal Form(s) and Specimen Processing Worksheet (with FedEx tracking #) to:
 
 
 ██████████	██████████████████	
 
 ██████████████████	██████████████████████████	
 
 ██████████	██████████████████████████████	
 
 ██████████████████	██████████████████████████████████	
 
 
Blood should be shipped priority overnight to:
 
██████████████████ ██████████████████████ ██████████████████████████ ██████████████████████████████ ██████████████████████████████ ██████████████████████████████ ██████████████████████████████████
	██████████	██████████████████	██████████████████	██████████████████████████	██████████	██████████████████████████████	██████████████████	██████████████████████████████████
██████████	██████████████████								
██████████████████	██████████████████████████								
██████████	██████████████████████████████								
██████████████████	██████████████████████████████████								

7.4.2 Stool Specimens

Please refer to the Specimen Collection Manual and video on the ACCL1633 page on the COG website for detailed instructions. Sites do not require special lab certification to process stool samples. However, local personnel collecting or processing study specimens should carefully review training references and forms.

Sample Time Points:
	
 • First day of conditioning or anytime within 72 hours before the start of conditioning (prior to chemotherapy) • Day 0 (graft infusion) • Day 7 post-transplant • Day 14 post-transplant • Day 28 post-transplant or discharge, whichever is first • Day 56 post-transplant • Day 120 post-transplant 
Sample acquisition can occur within 72 hours before the first day of conditioning. Sampling can occur within 24h before or after designated collection times for D0, D7, D14, D28 without being considered a protocol deviation. If the patient is not able to produce a stool sample in the appropriate time frame, obtain sample as soon as possible. This will not be considered a protocol deviation.
 
For D56 and D120 sample acquisition can occur within 14 days before or after the time point without being considered a deviation.

Supplies Required for Stool Collection & Processing:
	
The following stool specimens are required:
 
 A. 2 weighed Eppendorf vials (metabolomics) B. 4 cryovials (1.5 mL) for microbiome sequencing and long term storage 
Materials for Collection:
 
 A. Stool hats for collection B. Aliquot Vials 
 - 2 Eppendorf vials - 4 cryovials C. Scale (must weigh in increments of .001 grams) for weighing specimen for Eppendorf vials only D. Pipette (for watery stool) or scoop and/or orange stick (for solid stool) E. Gloves – must be worn at all times when handling stool and the vials. F. Mask (optional) G. Black, fine-tip Sharpie pen and Freezer-safe Labels (provided in kits)

Specimen Labeling:
	
Reminder: freezer-safe labels will be provided in specimen kits and must be used as specified in the Specimen Collection Manual. Each specimen must be legibly labeled with: ACCL1633, COG Patient ID#, Timepoint + Aliquot ID, and Collection Date.
 
For specimens placed in Eppendorf vials, weight before and after filling with stool must be documented on the Specimen Transmittal Form. Stool quality should be recorded on the Specimen Processing Worksheet. (See the Manual or Worksheet for stool quality classification guidelines.)

Specimen Processing:
	
Metabolomics (SCFA, bile acids, amino acids) For each sample:
 
 1. Weigh and record weight of two (2) empty Eppendorf vials separately; indicate weight on specimen forms. Indicate one Vial A and the second Vial B. Make sure Vial A and Vial B are labeled clearly (e.g. label the 2 vials collected on Start of Conditioning as: SOCA, SOCB). 2. Aliquot using a pipette or scoop and/or orange stick 50-150 mg of sample into each vial. Please do NOT exceed 150 mg of stool per aliquot. 3. Weigh and record weight of Vial A + sample, and Vial B + sample; enter each weight on specimen forms, separately. 4. Confirm that required labels are on each aliquot and that the details (i.e. the vial weights) are accurately recorded on the specimen forms. 5. Store aliquots at -80°C (-70°C is permitted). 
Microbiome Sequencing and Long-Term Storage (4 x 1.5 mL cryovials) For each of four (4) aliquots:
 
 1. Fill the cryovial using a pipette or scoop and/or orange stick with stool. 2. Tighten the lid back on the vial. 3. Place label on specimen aliquots and complete the specimen forms. 4. Store vials at -80°C (-70°C is permitted). 								

Specimen Packaging and Shipping:
	
Samples should remain frozen at -80°C (or -70°C) until ready for shipping. Batched shipment after a participant's completion of all seven time points is strongly encouraged. Be sure to include enough dry ice in the shipment to last 48 hours. Prior to shipment, the lab should be notified by e-mailing electronic copies of the Specimen Transmittal Form(s) and Specimen Processing Worksheet(s) (with FedEx tracking #) to:
 
 
██████████	████████████████████	
 
██████████████████	████████████████████	
 
██████████	████████████████████	
 
██████████████████	████████████████████	
 
 
Single or multiple patient specimens may be bulk shipped to the Microbiome center at Columbia University Medical Center. If sending samples on multiple patients, be sure each patient's samples are bagged separately and clearly labeled. All specimen shipments must include Specimen Transmittal Form(s) and Specimen Processing Worksheet.
 
██████████████████ ██ ██████████████████████████████████████ ██████████████████████████████████ ██████████████████████████████ ██ ██████████████████
	██████████	████████████████████	██████████████████	████████████████████	██████████	████████████████████	██████████████████	████████████████████
██████████	████████████████████								
██████████████████	████████████████████								
██████████	████████████████████								
██████████████████	████████████████████								

